7.1 DEMOGRAPHIC AND OTHER BASELINE CHARACTERISTICS

Only descriptive statistics are planned for this section of the report, based on the TS.

The data will be summarised by treatment sequence and in total.

7.2 CONCOMITANT DISEASES AND MEDICATION

Only descriptive statistics are planned for this section of the report, based on the TS.

Concomitant diseases will be coded using the coding system of the Medical Dictionary for Drug Regulatory Activities (MedDRA). Medications will be coded using the World Health Organization Drug Dictionary (WHO-DD). The coding version number will be displayed as a footnote in the respective output.

The diagnoses and medications will be listed. Subjects without any concomitant diagnoses or concomitant therapies should be marked with a “No” in the respective column.

The relevance of the concomitant therapies to the evaluation of PK will be decided no later than at the RPM.

7.3 TREATMENT COMPLIANCE

Only descriptive statistics are planned for this section of the report.

It is not intended to list the compliance separately. Any deviations from complete intake will be addressed in the RPM (see [Section 6.2](#)) and described in the CTR.

7.4 PRIMARY ENDPOINTS

For BI 1595043, the effect of food on the relative bioavailability will be investigated on the basis of the primary PK endpoints AUC_{0-tz} and C_{max} (see [Section 5.1](#))

7.4.1 Primary analysis of the primary endpoints

Section 7.3.1 of the CTP:

The statistical model used for the analysis of the primary endpoints will be an analysis of variance (ANOVA) model on the logarithmic scale. That is, the PK endpoints will be log-transformed (natural logarithm) prior to fitting the ANOVA model. This model will include effects accounting for the following sources of variation: sequence, subjects within sequences, period and treatment. The effect 'subjects within sequences' will be considered as random, whereas the other effects will be considered as fixed. The model is described by the following equation:

$$\begin{aligned} y_{ijkm} &= \mu + \zeta_i + s_{im} + \pi_j + \tau_k + e_{ijkm}, \text{ where} \\ y_{ijkm} &= \text{logarithm of response measured on subject } m \text{ in sequence } i \text{ receiving} \\ &\quad \text{treatment } k \text{ in period } j, \\ \mu &= \text{the overall mean,} \\ \zeta_i &= \text{the } i^{\text{th}} \text{ sequence effect, } i = 1, 2 \\ s_{im} &= \text{the effect associated with the } m^{\text{th}} \text{ subject in the } i^{\text{th}} \text{ sequence, } m = 1, 2, \dots, n_i \end{aligned}$$

π_j = the j^{th} period effect, $j = 1, 2$
 τ_k = the k^{th} treatment effect, $k = 1, 2$
 e_{ijkm} = the random error associated with the m^{th} subject in sequence i who received treatment k in period j .

where $s_{im} \sim N(0, \sigma_B^2)$ i.i.d., $e_{ijkm} \sim N(0, \sigma_W^2)$ i.i.d. and s_{im}, e_{ijkm} are independent random variables.

Point estimates for the ratios of the geometric means (test/reference) for the primary endpoints (see CTP Section 2.1) and their two-sided 90% confidence intervals (CIs) will be provided.

For each endpoint, the difference between the expected means for $\log(T)$ - $\log(R)$ will be estimated by the difference in the corresponding adjusted means (Least Squares Means). Additionally their two-sided 90% confidence intervals will be calculated based on the residual error from the ANOVA and quantiles from the t -distribution. These quantities will then be back-transformed to the original scale to provide the point estimate and 90% CIs for each endpoint.

The implementation for this analysis will be accomplished by using the CSD macros based on PKS. The following SAS code can be used:

```
PROC MIXED DATA=indata METHOD=REML;  
  CLASS subject treatment sequence period;  
  MODEL logpk = treatment sequence period / DDFM=KR;  
  RANDOM subject(sequence);  
  LSMEANS treatment / PDIFF CL ALPHA=0.1;  
RUN;
```

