#### 7.3.1 Primary endpoint analyses

#### Primary analyses

The statistical model used for the analysis of the primary endpoints will be an analysis of variance (ANOVA) model on the logarithmic scale. That is, the PK endpoints will be log-transformed (natural logarithm) prior to fitting the ANOVA model. This model will include effects accounting for the following sources of variation: sequence, subjects within sequences, period and treatment. The effect 'subjects within sequences' will be considered as random, whereas the other effects will be considered as fixed. The model is described by the following equation:

Page 57 of 75

Proprietary confidential information © 2021 Boehringer Ingelheim International GmbH or one or more of its affiliated companies

$$y_{ijkm} = \mu + \zeta_i + s_{im} + \pi_j + \tau_k + e_{ijkm}$$
, where

 $y_{ijkm}$  = logarithm of response measured on subject m in sequence i receiving treatment k in period j,

 $\mu$  = the overall mean,

 $\zeta_i$  = the ith sequence effect, i = 1, 2,

 $s_{im}$  = the effect associated with the  $m^{th}$  subject in the  $i^{th}$  sequence,  $m = 1, 2, ..., n_i$ 

 $\pi_j$  = the jth period effect, j = 1, 2,

 $\tau_k$  = the kth treatment effect, k = 1, 2,

 $e_{ijkm}$  = the random error associated with the  $m^{th}$  subject in sequence i who received treatment k in period j.

where  $s_{im} \sim N(0, \sigma_B^2)$  i.i.d.,  $e_{ijkm} \sim N(0, \sigma_W^2)$  i.i.d. and  $s_{im}$ ,  $e_{ijkm}$  are independent random variables.

Point estimates for the ratios of the geometric means (test/reference) for the primary endpoints (see Section 2.1) and their two-sided 90% confidence intervals (CIs) will be provided.

For each endpoint, the difference between the expected means for log(T)-log(R) will be estimated by the difference in the corresponding adjusted means (Least Squares Means). Additionally their two-sided 90% confidence intervals will be calculated based on the residual error from the ANOVA and quantiles from the t-distribution. These quantities will then be back-transformed to the original scale to provide the point estimate and 90% CIs for each endpoint.

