#### 7.7 DETERMINATION OF SAMPLE SIZE

It is planned to enter a total of 14 subjects in the trial, because this sample size is considered sufficient to achieve the aims of this exploratory trial. With this sample size, the following precision in estimating the ratio of geometric means (test/reference) can be expected with 95% probability. Precision is defined as the ratio of upper CI limit to the relative BA estimate. Note that the precision is independent of the actual ratio of geometric means.

Based on the previous SRD trial (see Section 1.2.5.2), the intra-individual coefficient of variation (gCV) for BI 1595043 is assumed to be roughly 23%.

For various assumptions around the gCV of 23%, Table 7.7: 1 provides an overview of the achievable precision for estimating the ratio of geometric means (test/reference). For

c34388550-04 Trial Protocol Proprietary confidential information © 2021 Boehringer Ingelheim International GmbH or one or more of its affiliated companies

structives may make a the expected 0.00% confidence intervals are displayed for a value of

illustrative purposes, the expected 90% confidence intervals are displayed for a value of 100% for the ratio T/R of geometric means.

Table 7.7: 1 Precision that can be expected with 95% probability and illustrative two-sided 90% confidence intervals around the ratio of geometric means (T/R) for different gCVs and sample sizes N in a 2x2 crossover trial

gCV [%]	N	Precision**	Ratio [%]*	Lower CL [%]	Upper CL [%]
	10	1.258		79.51	125.77
20	12	1.219	100	82.01	121.93
20	14	1.193	100	83.81	119.31
	16	1.174		85.18	117.40
	10	1.301	100	76.88	130.07
23	12	1.255		79.67	125.52
23	14	1.224		81.67	122.44
	16	1.202		83.20	120.19
	10	1.360	100	73.56	135.95
27	12	1.304		76.68	130.42
27	14	1.267	100	78.94	126.69
	16	1.240		80.67	123.97

^{*}Ratio of geometric means (test/reference) for a PK endpoint is defined by  $\exp(\mu_T)/\exp(\mu_R)$ .

The expected 90% confidence interval limits in the table were derived by

CI limit_{upper,lower} = 
$$exp(ln(\theta) \pm \omega)$$
,

with  $\theta$  being the ratio (T/R) on original scale and  $\omega$  the distance from the estimate  $\theta$  to either confidence interval limit on the log-scale, which was obtained from the achievable precision on the original scale.

The calculation was performed as described by Julious [R11-5230] using R Version 4.0.2.

^{**}Defined as ratio of upper CL and relative BA estimate.

c34388550-04 Trial Protocol Page 62 of 75

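### The SAP's primary PROC MIXED code bounds the subject variance at zero, so in some data sets it gives a narrower 90% CI than the ANOVA-residual interval the protocol defines

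*SAP*

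**What the plan says.** Protocol 7.3.1 specifies a log-scale ANOVA with sequence, subjects within sequences, period and treatment. The subject effect "will be considered as random, whereas the other effects will be considered as fixed". The interval is defined in words: "two-sided 90% confidence intervals will be calculated based on the residual error from the ANOVA and quantiles from the t-distribution". SAP 7.4.1 repeats this text.

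The SAP then says that the analysis will be run with company macros and shows code that may be used: "PROC MIXED DATA=indata METHOD=REML", then "MODEL logpk = treatment sequence period / DDFM=KR", a RANDOM statement for subject within sequence, and "LSMEANS treatment / PDIFF CL ALPHA=0.1". There is no NOBOUND option. Neither document says what happens if the subject variance is estimated as zero.

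SAP 7.4.2 repeats the analysis with all effects fixed (PROC GLM), as a sensitivity analysis. SAP Section 4 declares no change from the protocol's analyses.

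On variability, protocol 7.7 states that "the intra-individual coefficient of variation (gCV) for BI 1595043 is assumed to be roughly 23" percent, citing the single-rising-dose (SRD) trial. Table 1.2.5.2: 2 gives that trial's gCVs by dose group, with 6 active subjects per group. No between-subject variance is given anywhere.

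**The concern.** By default PROC MIXED does not let a variance component go below zero. In a complete 2x2 crossover the unconstrained REML estimate of the subject variance is (MSB - MSW)/2, where MSB and MSW are the between- and within-subject mean squares. If MSB is below MSW, the estimate is held at zero and the subject effect in effect leaves the model. The treatment contrast is then judged against a pooled variance on more degrees of freedom, which is not the residual error from the ANOVA.

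The primary CIs for AUC0-tz and Cmax are the main result of the trial, since no hypothesis test is specified. If the code and the written definition can give different intervals on the same data, the report needs a rule fixed in advance for which one is primary. Without it, the primary CI could disagree with the fixed-effects run in SAP 7.4.2 and be the narrower of the two, with nothing in the plan to explain why.

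**Working it through.** **Inputs.** N = 14, 1:1 allocation (protocol 7.6, 7.7), taken as 7 complete subjects per sequence. Intra-individual gCV 23% (protocol 7.7). SRD gCVs (Table 1.2.5.2: 2): AUC0-tz 20.1% at 25 mg and 20.2% at 50 mg; Cmax 26.2% at 25 mg and 27.1% at 50 mg. Variances are ln(1 + gCV²).

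**1. Reproduce the plan's precision.** Log half-width reached with 95% probability:

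ω = t(0.95, N-2) × √(2σ²w/N) × √(χ²(0.95, N-2)/(N-2))

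At 23%, σ²w = 0.0515, so ω = 1.782 × 0.0858 × √(21.03/12) = 0.2025. This gives 81.67% to 122.44% and precision 1.224, as in Table 7.7: 1. All 12 rows of the table match, so the planned precision rests on the ANOVA residual with N-2 df.

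**2. What the code returns on complete data.**

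| Case | Variance used | df | t(0.95) |
|---|---|---|---|
| MSB ≥ MSW | MSW | 12 | 1.782 |
| MSB < MSW | (MSB + MSW)/2 | 24 | 1.711 |

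In the second case the variance is below MSW and the t quantile is smaller. The ratio of log half-widths is therefore at most 1.711/1.782 = 0.960. A numerical bounded-REML fit of 1,500 simulated trials agreed with this rule every time.

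**3. How often.** P(boundary) = P(F(12,12) < σ²w/(σ²w + 2σ²b)). Because σ²b is not in the documents, it must be assumed. Treating the SRD gCV as total variability (parallel dose groups, one dose per subject) gives σ²b = max(0, ln(1 + gCV²) - 0.0515):

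- AUC0-tz, 25 mg: 0.0396 - 0.0515 is negative, so σ²b = 0. The same holds at 50 mg.
- Cmax, 25 mg: 0.0664 - 0.0515 = 0.0148 before rounding; F threshold 0.635.
- Cmax, 50 mg: 0.0709 - 0.0515 = 0.0193 before rounding; F threshold 0.572.

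Width, coverage and precision come from 2 million simulated trials per row:

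| Scenario (within gCV 23%) | Boundary | Mean half-width ratio at boundary | Overall coverage | 95%-probability precision |
|---|---|---|---|---|
| AUC0-tz, 25 mg | 50% | 0.87 | 88.1% | 1.194 |
| Cmax, 25 mg | 22.1% | 0.89 | 89.4% | 1.210 |
| Cmax, 50 mg | 17.3% | 0.90 | 89.5% | 1.213 |
| ANOVA-residual CI | n/a | 1 | 90.0% | 1.224 |

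**4. Sensitivity to the assumption.**

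- Equal between and within variances: F threshold 1/3, boundary 3.4%.
- Within gCV 15%, 25 mg SRD gCVs as total: 5.9% (AUC0-tz), 0.5% (Cmax).
- Within gCV 12%, same totals: 0.7% and 0.04%.
- SRD gCVs read as purely between-subject, within gCV 23%: 1.5% to 6%.

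**The case against.** **The frequency is not a plan figure.** This stands. It depends on subtracting 23% from SRD gCVs that come from 6 subjects per dose. The 50% end arises because the assumed within-subject CV exceeds the total AUC0-tz CV, which cannot be literally true. A parallel single-dose trial cannot yield an intra-individual CV. The mean of 20.1% and 26.2% is 23.15%, so the 23% may really be a total CV (an inference). The true within-subject CV would then be lower and the boundary rarer. A reader might infer that the plan's own figures imply the boundary in 22-50% of trials. They do not: that range uses only the 25 mg group and a between-subject variance that the plan never states.

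**The narrowed intervals do not themselves under-cover.** This also stands. A reader might infer that coverage is lost in the noisy data sets where the CI is shortened. In the boundary data sets the bounded CI covers 90.0% (AUC0-tz scenario) and 92.4% (Cmax, 25 mg), where the ANOVA CI covers 93.8% and 95.2%. The remaining trials cover 86.3% and 88.5%, and there both methods give the same interval. Only overall coverage falls below 90%.

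**No decision depends on it.** Largely true. The trial is exploratory and has no acceptance range, and the complete-data point estimate does not change. This limits the consequence but does not remove the mismatch.

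**It is already handled.** Only in part. The code is permissive and the macros are not shown, so the macro may behave differently. But this is the only primary implementation disclosed, and the GLM that gives the protocol's interval is labelled a sensitivity analysis.

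**Bounded REML respects the stated model.** A non-negative variance does fit the random-effects model in protocol 7.3.1. But the same section defines the CI by the ANOVA residual, and the sample-size table relies on that definition.

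**Conclusion.** The point holds as a mismatch between the written interval and the disclosed code. With 14 complete subjects the text means MSW on 12 df. The code switches to (MSB + MSW)/2 on 24 df whenever MSB is below MSW, and the log-scale CI is then at least 4% narrower, about 10-13% on average in the scenarios tabulated above.

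The frequency is conditional: about 17-50% of trials if 23% is the true within-subject gCV and the 25-50 mg SRD gCVs are total variability, with overall coverage of 88.1-89.5%. It is about 3% at equal variances and under 1% at a within-subject gCV of about 12% or lower. The documents cannot say which applies. All figures assume complete data and normal log-scale errors. The impact is modest, but the rule should be settled before results are seen.

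**What to change.** Add NOBOUND to the PROC MIXED statement in SAP 7.4.1, and confirm that the company macro does the same. Alternatively, name the fixed-subject model already coded in SAP 7.4.2 as the source of the primary CI. With complete data either choice gives exactly the protocol's interval. If some subjects contribute only one period, as the PKS definition allows, the two choices can differ, so the SAP should name one.

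The cost is one keyword or one sentence. No endpoint, sample size or data collection changes. The downside of NOBOUND is that a negative between-subject variance estimate may be printed. It is not an endpoint, and a footnote can explain it.

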7.4.2 Sensitivity analysis, subgroup analysis, exploratory analysis of the primary endpoints

Section 7.3.1 of the CTP: The same statistical model as stated above will be repeated for the primary endpoints but with all sources of variation ('sequence', 'subjects within sequences', 'period', 'treatment') considered as fixed effects.

The following SAS code can be used to fit the model:

```
PROC GLM DATA=indata;  
  CLASS subject treatment sequence period;  
  MODEL logpk = treatment subject(sequence) sequence period;  
  LSMEANS treatment / PDIFF CL ALPHA=0.1;  
  ESTIMATE 'T-R' treatment 1 -1;  
RUN;
```

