Reference product (R)	BI 1595043 as tablets (25 mg and 5 mg)
dose	30 mg
mode of admin.	Oral with 240 mL of water after an overnight fast of at least 10 h

30 June 2021

Boehringer Ingelheim BI Trial No.: 1445-0011 c34388550-04 Trial Protocol

234388550-04 Trial Protocol Page 3 of 75

Proprietary confidential information © 2021 Boehringer Ingelheim International GmbH or one or more of its affiliated companies

Duration of treatment	One day (single dose) for each treatment, separated by a washout period of at least 8 days
Statistical methods	Relative bioavailability will be estimated by the ratios of the geometric means (test / reference) for the primary and secondary endpoints. Additionally, their two-sided 90% confidence intervals (CIs) will be provided. This method corresponds to the two one-sided t-test procedure, each at a 5% significance level. Since the main focus is on estimation and not testing, a formal hypothesis test and associated acceptance range is not specified. The statistical model will be an analysis of variance (ANOVA) on the logarithmic scale including effects for sequence, subjects nested within sequences, period and treatment. CIs will be calculated based on the residual error from the ANOVA and quantiles from the t-distribution. Descriptive statistics will be calculated for all endpoints.

c34388550-04 Trial Protocol Page 4 of 75

Proprietary confidential information © 2021 Boehringer Ingelheim International GmbH or one or more of its affiliated companies

FLOW CHART

Period	Visit	Day	Planned time (relative to drug administration th:minl	Approximate clock time of actual day [h:min]	Event and comment	Safety laboratory ⁷	PK blood 9,14	12-lead ECG ¹⁰	Vital signs (BP, PR) ¹³	Questioning for AEs and concomitant therapy ⁶
SCR	1	-21 to -1			Screening ¹	A		X	x ¹¹	
	2/3	-3 to -1 ⁸	-72:00	08:00	Ambulatory visit ⁸	В			x ¹¹	X
		-1	-14:00	18:00	Admission to trial site ¹²	x ⁵				
(su		1	-02:00	06:00	Allocation to treatment (visit 2 only) ²		x ²	X ²	x ^{2,11}	x ²
stratio			-00:30	07:30	High fat, high calorie breakfast (only in treatment T2)					
ninis			00:00	08:00	Drug administration					
adn			00:15	08:15			X			
lrug			00:30	08:30			X			
en d			00:45	08:45			X			
twe			01:00	09:00			X	X	X	X
s pe			01:15	09:15			X			
day			01:30	09:30			X			
st 8			02:00	10:00	240 mL fluid intake ³		X		X	X
t lea			02:30	10:30			X			
ofa			03:00	11:00			X			
out			04:00	12:00	240 mL fluid intake, thereafter lunch ³		X		X	X
/ash			06:00	14:00			X			

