6. GENERAL ANALYSIS DEFINITIONS

6.1 TREATMENTS

For basic study information on treatments to be administered, assignment of treatment groups, selection of doses, refer to CTP Section 4.

The study will be performed as a randomised, open-label, two-way cross-over trial. The treatments will be one single dose of 30 mg of BI 1595043 administered as tablets in the fasting state (R) and one single dose of 30 mg of BI 1595043 administered as tablets in the fed state (T). In total, it was planned to assign 14 healthy male subjects to the 2 treatment sequences RT or TR.

There will be a washout period of at least 8 days between the treatments.

For details of dosage and formulation see Table 6.1: 1 below:

Table 6.1: 1 Treatments and labels used in the analysis

Treatment	Short label
R BI 1595043, 1*5mg + 1*25 mg film coated tablets, qd, fasted	BI 30mg fast
T BI 1595043, 1*5mg + 1*25 mg film coated tablets, qd, fed	BI 30mg fed

Section 1.2.6 of CTP:

The residual effect period (REP) for BI 1595043, when measurable drug levels or PD effects are still likely to be present after the last administration, is about 6 days (estimated based on 5 times terminal $t_{1/2}$ of dose group 5 of up to 29.3 h). Conservatively, all AEs reported until the end of trial examination will be considered on treatment.

The following study phases will be defined for the analysis of adverse events (AEs):

- **Screening**
 - Ranging from 0:00h on day of informed consent until administration time of study medication in treatment period 1.
- **On treatment** (labelled “BI 30mg fast”, “BI 30mg fed”)
 - Ranging from the administration time of BI 1595043 until next administration time or until 0:00 h on day after trial termination date (whatever occurs first)

Section 7.3.4 of the CTP: *Note that AEs occurring after the last per protocol contact but entered before final database lock will be reported to Pharmacovigilance only and will not be captured in the trial database.*

The following AE displays will be provided in the report:

A) Section 15.3 and Appendix 16.1.13.1.8 (for ClinicalTrials.gov and EudraCT only) of the CTR displays:

In these displays, the on treatment phase will be analysed (labelled with the name of the study treatment (short label)). Screening will not be included in this analysis.

The following total will be provided in addition (Section 15.3 only):

- a total over all on treatment phases included in this analysis ("Total")

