B) Section 15.4 and Appendix 16.1.13.1.8 (except for ClinicalTrials.gov and EudraCT) of the CTR displays:

- Screening
- On treatment (labelled with the name of the study treatment (short label))

In Section 16.1.13.1.8 AE tables, the following total will be provided in addition:

- a total over all study phases ("Total")

In Appendix 16.2 (Listings) of the CTR displays, screening will be included and no totals will be provided.

For detailed information on the handling of the treatments, refer to Technical TSAP ADS plan and Analysis Data Reviewers guide.

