7. PLANNED ANALYSIS

Safety analysis (refer to [Section 7.8](#)) will be performed by [REDACTED] and will be presented in Sections 15.1 to 15.4 of the CTR and in Appendix 16.2 and 16.1.13.1.

Inferential statistical analyses of PK endpoints (refer to [Section 7.4](#) and [Section 7.5.2](#)) will also be performed by [REDACTED] and will be presented in Section 15.5 of the CTR and in Appendix 16.1.13.3.

Descriptive data analysis of PK endpoints and concentrations will be performed by the [REDACTED] at [REDACTED] and will be presented in Section 15.6 of the CTR.

The format of the listings and tables will follow the BI standards (see BI-KMED-BDS-HTG-0045 ([6](#)) with the exception of those generated for PK-calculations following BI standards for PK/PD analysis ([7](#)).

The individual values of all subjects will be listed, sorted by treatment sequence, subject number and visit. The listings will be included in Appendix 16.2 of the CTR.

For End-Of-Text (EoT) tables, the set of summary statistics is:

N	number non-missing observations
Mean	arithmetic mean
SD	standard deviation
Min	minimum
Median	median
Max	maximum

For analyte concentrations, the following descriptive statistics will additionally be calculated:

CV	arithmetic coefficient of variation
gMean	geometric mean
gCV	geometric coefficient of variation

For PK parameters, the following descriptive statistics will additionally be calculated:

CV	arithmetic coefficient of variation
gMean	geometric mean
gCV	geometric coefficient of variation
P10	10th percentile
Q1	1st quartile
Q3	3rd quartile
P90	90th percentile

The data format for descriptive statistics of concentrations will be identical to the data format of the respective concentrations. The descriptive statistics of PK parameters will be calculated

using the individual values with the number of decimal places as provided by the evaluation program. Then the individual values as well as the descriptive statistics will be reported with three significant digits in the CTR.

Tabulations of frequencies for categorical data will include all possible categories and will display the number of observations in a category as well as the percentage (%) relative to the respective treatment group (unless otherwise specified, all subjects in the respective subject set whether they have non-missing values or not).

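### The sensitivity-analysis contrast labelled T-R returns R minus T under default SAS ordering with the SAP's own treatment labels, and the coding of the treatment variable is not stated

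*SAP*

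**What the plan says.** Protocol 7.3.1, repeated in SAP 7.4.1, fixes the direction of the effect: "the difference between the expected means for log(T)-log(R) will be estimated by the difference in the corresponding adjusted means". The result is back-transformed to a test/reference ratio. Test (T) is the fed state and reference (R) the fasted state (Protocol 2.1.1).

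SAP 7.4.2 repeats the model with all effects fixed and offers PROC GLM code. Its CLASS statement lists subject, treatment, sequence and period. There is no ORDER= or REF= option. The contrast is "ESTIMATE 'T-R' treatment 1 -1".

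The documents label the treatments as follows:

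- SAP Table 6.1: 1 uses the letters R and T with full texts, the reference entry being "R BI 1595043, 1*5mg + 1*25 mg film coated tablets, qd, fasted"; the test entry ends in 'fed'. The short labels are `BI 30mg fast` and `BI 30mg fed`.
- The Protocol Flow Chart calls the fed treatment T2: "High fat, high calorie breakfast (only in treatment T2". It prints no partner label.

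The SAP does not state which values `treatment` takes in `indata`. SAP 6.1 points elsewhere: "For detailed information on the handling of the treatments, refer to Technical TSAP ADS plan and Analysis Data Reviewers guide".

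**The concern.** In an ESTIMATE statement the coefficients apply to the CLASS levels in their sorted order. The text in quotation marks is only a printed label and does not affect the calculation. If R sorts before T, coefficients 1 and -1 give R minus T on a line that says T-R.

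The direction of the food effect is what this trial sets out to learn. Read at face value, the sensitivity line would show a fed-state increase as a decrease, or the reverse, and would appear to contradict the primary analysis.

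Comparing the line with the pairwise difference from the same PROC GLM step would not expose the problem. That difference is also first level minus second, so the two would agree in sign. Only the treatment least-squares means or the descriptive geometric means would show it, and the SAP does not ask for that comparison.

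**Working it through.** **Assumption about the software.** With no ordering option, SAS sorts CLASS levels in ascending order of their formatted values. This is standard SAS behaviour and is not stated in the documents. SAS itself was not run; the model was rebuilt outside it.

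**Step 1: sort order of the labels**

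| Labels (fasted / fed) | Source | First level | Coefficients 1 -1 give |
|---|---|---|---|
| R / T | Protocol 2.1.1, SAP Table 6.1: 1 | R | R minus T |
| Reference / Test | Protocol 2.1.1, Protocol Table 4.1.4: 1 | Reference | R minus T |
| `BI 30mg fast` / `BI 30mg fed` | SAP Table 6.1: 1 | fast ('a' before 'e') | R minus T |
| Full texts, with or without the leading letter | SAP Table 6.1: 1 | fasted | R minus T |
| T1 / T2 | Flow Chart gives T2 only; T1 is assumed | T1 | R minus T |
| 2 / 1 (numeric, fed = 1) | Counter-case, not in the documents | fed | T minus R |

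**Step 2: fit of the SAP model.** The fixed-effects model (treatment, subject within sequence, sequence, period) was fitted to simulated two-period crossover data with N = 14 and gCV 23%. Contrast (1, -1) was applied to the sorted levels.

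| True T/R | Code as written, levels R, T | Coefficients -1 1 |
|---|---|---|
| 0.80 | +0.3136; ratio 1.368 (90% CI 1.275 to 1.468) | -0.3136; ratio 0.731 (0.681 to 0.784) |
| 1.25 | -0.2125; ratio 0.809 (0.678 to 0.964) | +0.2125; ratio 1.237 (1.038 to 1.474) |

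The right-hand column is the T/R estimate in each simulated sample. The degrees of freedom are 12 either way, and each pair of intervals is reciprocal. With two subjects lacking period 2, the sign flips in the same way: 1.275 as written against 0.785 with T first.

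**Step 3: size at the protocol's own precision.** In Protocol 7.7, "the intra-individual coefficient of variation (gCV) for BI 1595043 is assumed to be roughly 23" per cent, and Table 7.7: 1 prints a precision of 1.224 for N = 14. This reproduces from

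precision = exp{ t(0.95, n-2) × √[ (2 ln(1+gCV²)/n) × χ²(0.95, n-2)/(n-2) ] }

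- 2 ln(1+0.23²)/14 = 2 × 0.05155/14 = 0.007364
- χ²(0.95, 12)/12 = 21.026/12 = 1.752
- √(0.007364 × 1.752) = 0.1136
- exp(1.782 × 0.1136) = 1.2244

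The other 11 rows of the table reproduce too. Applied to two illustrative results:

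- Observed T/R 125%: the limits are 1.25/1.2244 = 102.1% and 1.25 × 1.2244 = 153.1%. Inverted, the ratio is 1/1.25 = 80.0%, with limits 1/1.531 = 65.3% and 1/1.021 = 98.0%.
- Observed T/R 70%: the limits are 0.70/1.2244 = 57.2% and 0.70 × 1.2244 = 85.7%. Inverted, the ratio is 142.9%, with limits 116.7% and 174.9%.

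**Step 4: the primary code.** SAP 7.4.1 uses PROC MIXED with "LSMEANS treatment / PDIFF CL ALPHA=0.1" and no ESTIMATE line. Its output identifies the levels, so nothing is mislabelled. Under the same ordering its difference also runs R minus T and needs its sign reversed before back-transformation.

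**The case against.** The strongest objection is that the coding of `indata` cannot be seen. The SAP defers treatment handling to other files, the labels in Table 6.1: 1 may be for display only, and the model's index k = 1, 2 does not say which treatment is 1. If T sorts first, the line is correct and -1 1 would be wrong. That stands as a condition on the finding. It does not clear the line: no coding that puts T first appears in either document, and every complete label pair makes the line wrong. The T2 label supports this only under the assumption about T1.

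Further points limit the consequence:

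- The code is offered as code that can be used, while the governing text fixes T minus R. That is true, but sample code is there to be copied.
- The ESTIMATE line requests no confidence limits. Only its point estimate is directly mislabelled. The inverted intervals above arise if the limits from the pairwise-difference line, which run in the same R minus T direction, are reported under the T-R label.
- The treatment least-squares means in the same step, or the planned geometric means, would reveal the reversal. That is so if someone compares them.
- This is a sensitivity analysis, and Protocol 7.2 sets no formal test or acceptance range. No formal decision turns on it.

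These points make it a correction to sample code, not a threat to the primary result.

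**Conclusion.** The concern holds. With default level ordering and any complete pair of treatment labels in the documents, the line labelled T-R in SAP 7.4.2 estimates log(R)-log(T), and its back-transformed ratio is the exact reciprocal of the planned one (125% reads as 80.0%). The standard error, degrees of freedom and log-scale interval width are unaffected, and the primary PROC MIXED code is not mislabelled.

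The conclusion rests on default SAS ordering, which is near certain because the code sets no option. It also rests on `indata` using a coding that sorts like the documented labels, which is likely but not stated. If T sorts first there is no error. The line should be fixed before the code is used.

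**What to change.** 1. State in SAP 7.4 how `treatment` is coded in `indata` and the resulting level order.
2. For levels ordered R, T, change the line to `ESTIMATE 'T-R' treatment -1 1;`. If wanted, put the same explicit contrast in the PROC MIXED code so that both analyses report T minus R directly.
3. Add a check that the sign of the estimate agrees with the treatment least-squares means, or with the geometric means already planned in SAP 7 ("For PK parameters, the following descriptive statistics will additionally be calculated").

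No CLPARM option is needed, because the LSMEANS line already requests the 90% interval; its direction must be reported as T minus R. The cost is one code line and a sentence or two in the SAP, with no effect on data, subjects or timelines.
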